8.3 Emergency unblinding of treatment assignment

Not applicable as this is an open label study.

8.4 Pregnancies

This trial is planned for men, post-menopausal women or premenopausal women with ovarian suppression. No pregnancies are expected for study patients. If a female trial participant becomes pregnant, the study treatment should be stopped, and the pregnancy consent form should be presented to the trial participant. The participant must be given adequate time to read, review and sign the pregnancy consent form. The consent form is necessary to allow the investigator to collect and report information regarding the pregnancy.

To ensure patient safety, each pregnancy occurring while the patient is on study treatment must be reported to Novartis within 24 hours of learning of its occurrence. The pregnancy should be followed up to determine outcome, including spontaneous or voluntary termination, details of the birth, and the presence or absence of any birth defects, congenital abnormalities, or maternal and/or newborn complications.

Pregnancy should be recorded on a Clinical Trial Pregnancy Form and reported by the investigator to the Novartis Chief Medical Office and Patient Safety (CMO&PS). Pregnancy follow-up should be recorded on the same form and should include an assessment of the possible relationship to the study treatment any pregnancy outcome. Any SAE experienced during pregnancy must be reported on the SAE Report Form.

Pregnancy outcomes should be collected for the female partners of any males who took study treatment in this study. Consent to report information regarding these pregnancy outcomes should be obtained from the mother.

After consent is provided, the pregnancy reporting will occur up to one year after the estimated date of delivery.

8.5 Warnings and precautions

No evidence available at the time of the approval of this study protocol indicated that special warnings or precautions were appropriate, other than those noted in the provided Investigator Brochure. Additional safety information collected between IB updates will be communicated in the form of Investigator Notifications. This information will be included in the patient informed consent and should be discussed with the patient during the study as needed.

8.6 Data Monitoring Committee

Not applicable.

8.7 Steering Committee

A Steering Committee (SC) will be established comprising investigators and Novartis personnel participating in the trial to ensure transparent management of the trial according to the protocol. The details of the steering committee, including roles will be defined in a steering committee charter.

A Novartis Safety Management Team (SMT) periodically reviews and evaluates all emerging data across the alpelisib program for potential safety signal assessment in a timely manner.

9 Data collection and management

9.1 Data confidentiality

Information about study subjects will be kept confidential and managed under the applicable laws and regulations. Those regulations require a signed subject authorization informing the subject of the following:

- What protected health information (PHI) will be collected from subjects in this study
- Who will have access to that information and why
- Who will use or disclose that information
- The rights of a research subject to revoke their authorization for use of their PHI

In the event that a subject revokes authorization to collect or use PHI, the investigator, by regulation, retains the ability to use all information collected prior to the revocation of subject authorization. For subjects that have revoked authorization to collect or use PHI, attempts should be made to obtain permission to collect follow-up safety information (e.g. has the subject experienced any new or worsened AEs) at the end of their scheduled study period.

The data collection system for this study uses built-in security features to encrypt all data for transmission in both directions, preventing unauthorized access to confidential participant information. Access to the system will be controlled by a sequence of individually assigned user identification codes and passwords, made available only to authorized personnel who have completed prerequisite training.

9.2 Site monitoring

Before study initiation, at a site initiation visit or at an investigator's meeting, Novartis personnel (or designated CRO) will review the protocol and eCRFs with the investigators and

their staff. During the study, the field monitor will visit the site regularly to check the completeness of patient records, the accuracy of entries on the eCRFs, the adherence to the protocol to Good Clinical Practice, the progress of enrollment, and to ensure that study treatment is being stored, dispensed, and accounted for according to specifications. Key study personnel must be available to assist the field monitor during these visits.

The investigator must maintain source documents for each patient in the study, consisting of case and visit notes (hospital or clinic medical records) containing demographic and medical information, laboratory data, electrocardiograms, and the results of any other tests or assessments. All information recorded on eCRFs must be traceable to source documents in the patient's file. The investigator must also keep the original signed informed consent form (a signed copy is given to the patient).

The investigator must give the monitor access to all relevant source documents to confirm their consistency with the eCRF entries. Novartis monitoring standards require full verification for the presence of informed consent, adherence to the inclusion/exclusion criteria and documentation of SAEs. Additional checks of the consistency of the source data with the eCRFs are performed according to the study-specific monitoring plan.

9.3 Data collection

For studies using Electronic Data Capture (EDC), the designated investigator staff will enter the data required by the protocol into the Electronic Case Report Forms (eCRF). The eCRFs have been built using fully validated secure web-enabled software that conforms to 21 CFR Part 11 requirements, Investigator site staff will not be given access to the EDC system until they have been trained. Automatic validation programs check for data discrepancies in the eCRFs and, allow modification or verification of the entered data by the investigator staff.

The Principal Investigator is responsible for assuring that the data entered into eCRF is complete, accurate, and that entry and updates are performed in a timely manner.

9.4 Database management and quality control

For studies using eCRFs, Novartis personnel (or designated CRO) will review the data entered by investigational staff for completeness and accuracy. Electronic data queries stating the nature of the problem and requesting clarification will be created for discrepancies and missing values and sent to the investigational site via the EDC system. Designated investigator site staffs are required to respond promptly to queries and to make any necessary changes to the data.

Concomitant treatments and prior medications entered into the database will be coded using the WHO Drug Reference List, which employs the Anatomical Therapeutic Chemical classification system. Medical history/current medical conditions and adverse events will be coded using the Medical dictionary for regulatory activities (MedDRA) terminology.

Samples and/or data will be processed centrally and the results will be sent electronically to Novartis (or a designated CRO).

Data about all study treatments dispensed to the patient and all IRT assigned dosage changes will be tracked using an Interactive Response Technology. The system will be supplied by a

vendor(s), who will also manage the database. The data will be sent electronically to Novartis personnel (or designated CRO).

For EDC studies, after database lock, the investigator will receive a CD-ROM or paper copies of the patient data for archiving at the investigational site.

10 Statistical methods and data analysis

The primary analysis for each cohort will be performed 6 months after the last patient enrolled in that specific cohort has started treatment. The final analysis will be performed after LPLV of the study which include cumulative data (eg safety and clinical benefit) since the Core Phase analysis.

Prior to the final analysis, cohort specific analyses maybe performed when all patients included in the corresponding cohort have approximately 18 months of follow-up.

The data will be analyzed by Novartis and/or a designated CRO. Any data analysis carried out independently by an investigator should be submitted to Novartis before publication or presentation. The data from all centers that participate in this study will be combined in the final safety and efficacy analysis.

10.1 Analysis sets

10.1.1 Full analysis Set

The Full Analysis Set (FAS) comprises all patients to whom study treatment has been assigned and who received one dose of study treatment. Patients will be analyzed according to the treatment they have been assigned to.

Modified full analysis set

The modified Full Analysis Set (mFAS) comprises all patients of the FAS population who have PIK3CA mutation confirmed by a Novartis designated laboratory. mFAS will be the primary population for the analysis of efficacy endpoints.

10.1.2 Safety set

The Safety Set includes all patients who received at least one dose of study treatment. Patients will be analyzed according to the study treatment received, where treatment received is defined as the assigned treatment if the patient took at least one dose of that treatment.

10.1.3 Per-protocol set

The Per-Protocol Set (PPS) consists of a subset of the patients in the mFAS who are compliant with requirements of the clinical study protocol. All protocol deviations or conditions leading to exclusion from the PPS will be detailed in the data handling plan and statistical analysis plan. Sensitivity analyses of the primary endpoint may be performed using PPS.

10.1.4 Dose-determining analysis set

Not applicable.

10.1.5 Pharmacokinetic analysis set

Not applicable.

10.1.6 Other analysis sets

Not applicable.

10.2 Patient demographics/other baseline characteristics

The FAS will be used for the analyses below and repeated on mFAS for demographic characteristics.

Demographic and other baseline data including disease characteristics will be listed and summarized descriptively.

Categorical data, such as gender, race will be presented by contingency type tables. Descriptive summary statistics (e.g. frequency, mean, median, range and standard deviation) will be used to present continuous data.

Relevant medical histories and current medical at baseline will be summarized separately by system organ class and preferred term in each cohort.

10.3 Treatments (study treatment, concomitant therapies, compliance)

The Safety set will be used for the analyses below.

Categorical data will be summarized as frequencies and percentages. For continuous data, mean, standard deviation, median, 25th – 75th percentiles, minimum, and maximum will be presented.

The duration of exposure (in months) to "investigational drug" and combination partner (fulvestrant and letrozole) as well as the dose intensity will be summarized by means of descriptive statistics using the safety set. The duration of exposure will also be presented for the study treatment by cohort. The number of subjects with dose adjustments (reduction, interruption, or permanent discontinuation) and the reasons will be listed and summarized by cohort.

Concomitant medications taken concurrently with the study drugs will be listed and summarized by Anatomical Therapeutic Chemical Classification System (ATC) term, preferred term by means of frequency counts and percentages in each cohort. Surgical and medical procedures will be coded using MedDRA and summarized by SOC and preferred term in each cohort. These summaries will include therapy starting on or after the start of study treatment (defined as Cycle 1 Day 1) or therapy starting prior to the start of study treatment and continuing after the start of study treatment.

Any prior concomitant medications or significant non-drug therapies starting and ending prior to the start of study treatment will be listed.

10.4 Primary objective

The primary objective of the study is to assess the proportion of patients who are alive without disease progression at 6 months based on local investigator assessment per RECIST v1.1 separately in Cohorts A and C (alpelisib in combination with fulvestrant) and Cohort B (alpelisib in combination with letrozole) among patients with HR+, HER2-negative aBC harboring a PIK3CA mutation who have progressed on or after prior treatments.

The mFAS will be used for the primary efficacy analysis.

10.4.1 Variable

The primary efficacy endpoint is the proportion of patients who are alive without disease progression at 6 months based on local investigator assessment using RECIST v1.1 in each cohort.

10.4.2 Statistical hypothesis, model, and method of analysis

A proportion of patients alive without progression after 6 months is considered as a clinically meaningful threshold in all the cohorts for this study. Therefore, evidence of treatment effect will be tested using the following hypothesis:

H₀:

Where p is the proportion of patients who are alive without progression at 6 months.

The primary endpoint will be presented together with two-sided 95% confidence intervals using Clopper and Pearson (1934) exact method for all the cohorts separately. The null hypothesis will be rejected and evidence of treatment effect will be demonstrated if the lower bound of the 95% CI for observed proportion at 6 months is greater than Table 10-1 displays the values of proportion of patients who are alive without any disease progression at 6 months and its 95% CI for selected number of patients alive without progressive disease out of 112 patients. To reject the null hypothesis at least 44 patients need to be alive without progression at 6 months out of 112 patients in each cohort.

Table 10-1 Exact 95% Confidence Interval

Sample size	Number of patients alive without PD at 6 months	Proportion k/N (%)	Exact 95% Co (CI)	onfidence Interval
	(k)		Lower (%)	Upper (%)
112				

10.4.3 Handling of missing values/censoring/discontinuations

Six months is defined in this study as $24 \text{ weeks} \pm 1 \text{ week}$. Therefore tumor assessments between week 23 and 25 will be considered for the primary analysis. For primary endpoint analysis, patients who progressed, died, or discontinued study before 6 months will be counted as a "failure".

10.4.4 Supportive and Sensitivity analyses

The primary analysis will also be performed on the FAS and may be repeated on PPS.

The primary analysis will also be repeated in patients from mFAS harboring a PIK3CA mutation as determined via ctDNA.

10.5 Secondary objectives

The secondary objectives in this study are to evaluate the progression free survival (PFS), progression free survival 2 (PFS2), overall response rate (ORR), clinical benefit rate (CBR), overall survival (OS) and duration of response (DOR), and safety. For efficacy secondary objectives, 95% confidence intervals will be provided as needed.

The secondary efficacy analysis will also be repeated in patients harboring a PIK3CA mutation as determined via ctDNA.

10.5.1 Secondary efficacy objective(s)

10.5.1.1 Progression free survival

PFS is defined as the time from the date of first dose of study medication to the date of the first documented progression or death due to any cause occurring in the study. PFS will be assessed based on local investigator's assessment according to RECIST v1.1 (see Appendix 5 for further details).

PFS will be censored if no PFS event is observed before the cut-off date. The censoring date will be the date of last adequate tumor assessment before the cut-off date. If a PFS event is observed after two or more missing or non-adequate tumor assessments, then PFS will be censored at the last adequate tumor assessment. If a PFS event is observed after a single missing or non-adequate tumor assessment, the actual date of event will be used (see Appendix 5). It is not intended to censor patients for new anticancer therapy prior to documented disease progression in the primary analysis.

The Kaplan-Meier estimate of the PFS survival function will be estimated and displayed. The resulting median PFS time will be given for each cohort with 95% confidence intervals, as well as 25th and 75th percentiles will be reported.

10.5.1.2 Progression free survival 2

PFS2 is defined as time from the date of first dose of study medication to the date of first documented progression on next-line therapy or death from any cause.

The first documented progression on next-line treatment is based on investigator assessment of PD (i.e. as captured on the anti-neoplastic therapy after treatment discontinuation eCRF page);

it is not necessary to continue to collect tumor assessments data for subsequent anti-neoplastic therapies for the purpose of PFS2.

PFS2 will be summarized using the Kaplan-Meier method on the mFAS. The resulting median PFS will be given with 95% confidence intervals for each cohort.

10.5.1.3 Overall response rate

ORR is defined as the proportion of patients with best overall response (BOR) of CR or partial response (PR), as per local investigator's assessment and according to RECIST v1.1 (see Appendix 5 for details). Patients with non-measurable lesions only at baseline will be included as 'responders' if they achieve a CR, otherwise they will be included as 'non-responders'.

ORR will be calculated based on the mFAS. ORR and its exact 95% confidence interval (Clopper and Pearson 1934) will be presented for each cohort.

10.5.1.4 Clinical benefit rate

Clinical Benefit Rate is defined as the proportion of patients with a best overall response of CR or PR or an overall lesion response of stable disease (SD) or Non-CR/ Non-PD lasting ≥ 24 weeks based on local investigator's assessment according to RECIST v1.1.

CBR will be calculated based on the mFAS. The CBR and its exact 95% confidence interval (Clopper and Pearson 1934) will be provided for each cohort.

10.5.1.5 Duration of response

DOR is the time from the date of first documented response (confirmed CR or PR) to the date of first documented progression or death due to underlying cancer. DOR only applies to patients whose best overall response is CR or PR according to RECIST v1.1 based on tumor response data per local investigator's assessment. The start date is the date of first documented response of CR or PR (i.e., the start date of response, not the date when response was confirmed), and the end date is defined as the date of the first documented progression or death due to underlying cancer. Patients continuing without progression or death due to underlying cancer will be censored at the date of their last adequate tumor assessment.

DOR will be listed and summarized for each cohort in the mFAS with confirmed BOR of CR or PR. DOR will be summarized using Kaplan-Meier estimates in patients with confirmed CR or PR within each cohort.

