2.6.4 Rationale for Public Health Emergency mitigation procedures

During a Public Health emergency as declared by Local or Regional authorities i.e. pandemic, epidemic or natural disaster, mitigation procedures to ensure participant safety and trial integrity are listed in relevant sections. Notification of the Public health emergency should be discussed with Novartis prior to implementation of mitigation procedures, and permitted/approved by Local or Regional Health Authorities and Ethics Committees as appropriate.

3 Objectives and endpoints

Objectives and related endpoints are described in Table 3-1 below.

Table 3-1 Objectives and related endpoints

Objective	Endpoint	Analysis
Primary		Refer to Section 10.4
To assess the proportion of patients who are alive without disease progression at 6 months based on local investigator assessment per RECIST v1.1 separately in cohorts A and C (alpelisib in combination with fulvestrant) and cohort B (alpelisib in combination with letrozole) among patients with HR+, HER2-negative aBC harboring a PIK3CA mutation who have progressed on or after prior treatments.	The primary endpoint of this study is the proportion of patients who are alive without disease progression at 6 months based on local investigator assessment using RECIST v1.1 in each cohort	
Secondary		Refer to Section 10.5
To assess PFS based on local investigator assessment for each cohort.	PFS based on local investigator assessment using RECIST v1.1 in each cohort	
To assess PFS on next-line treatment (PFS2) for each cohort.	PFS2 based on local investigator assessment in each cohort	
To assess overall response rate (ORR) and clinical benefit rate (CBR) based on local investigator assessment for each cohort.	ORR based on local investigator's assessment according to RECIST v1.1 in each cohort Clinical Benefit Rate (CBR) based on local investigator's assessment according to RECIST v1.1 in each cohort	
To assess duration of response (DOR) in patients with confirmed complete response (CR) or PR for each cohort.	Duration of Response is the time from the date of first documented response (confirmed CR or PR) to the date of first documented progression or death	
To assess Overall Survival (OS) for each cohort	Overall Survival is defined as the time of start of treatment to date of death or lost to follow-up.	

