10.5.1.6 Overall Survival

All patients should be followed until death or until patient has had adequate follow-up time as specified in the protocol whichever comes first. The follow-up data should contain the date the patient was last seen alive / last known date patient alive, the date of death and the reason of death ("Study indication" or "Other").

OS is defined as the time from date of start treatment to date of death due to any cause. If a patient is not known to have died, then OS will be censored at the date of last known date patient alive.

The analyses for OS will be based on the FAS. The distribution function of OS will be estimated using the Kaplan-Meier method. The median OS along with 95% confidence intervals will be presented for each cohort.

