enrollment, allowing for the +1 week visit window for tumor assessments. Patients with only non-measurable disease at baseline will be part of the analysis and will be included in the numerator only if they achieve a complete response or have a 'Non-CR/Non-PD' response 23 weeks or more after start of study treatment. CBR will be calculated using the mFAS based on the investigators' tumor assessments.

Duration of response

Duration of response (DOR) only applies to patients whose best overall response is complete response (CR) or partial response (PR) according to RECIST 1.1 based on local investigators review of tumor assessment data. The start date is the date of first documented response of CR or PR (i.e., the start date of response, not the date when response was confirmed), and the end date is defined as the date of the first documented progression or death due to underlying cancer. Patients continuing without progression or death due to underlying cancer will be censored at the date of their last adequate tumor assessment using the censoring rule described for PFS analysis (options A(1), C2(1), D(1), E(1), F(1-3) and G(1) from Table 3-2 in Appendix 5 of the study protocol).

Overall Survival

OS is defined as the time from date of start treatment to date of death due to any cause. If a patient is not known to have died, then OS will be censored at the date of last known date patient alive.

PFS after next-line of treatment (PFS2)

PFS2 is defined as time from date of start of treatment to the first documented disease progression (clinical or radiologic) on next-line therapy or death from any cause, whichever occurs first. The first documented progression on next-line treatment will be based on investigator assessment of PD (i.e. as captured on the anti-neoplastic therapy after treatment discontinuation CRF page).

1. Next-line therapy is defined as the first new (systemic) anti-neoplastic therapy initiated after discontinuation of study treatment regardless of EoT reason. Drugs given as part of the same regimen should be grouped as one line (i.e. part of the next-line therapy). In addition, continuation of the study treatment after the initial radiologic disease progression will not be considered as next-line therapy.
2. PFS2 will be censored if no PFS2 event (progression or death) is observed during next-line therapy before the analysis cut-off date; the censoring date will be the last contact date.

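### Duration of response ends at any death in the objectives tables but only at cancer death in the analysis sections, and the SAP presents the narrower rule as the PFS rule

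*Protocol*

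**What the plan says.** **Objectives tables.** Protocol Table 3-1 runs DOR from first documented response ("confirmed CR or PR) to the date of first documented progression or death"). Table 1-1 of the main SAP (Amendment 4) has the same wording. Neither qualifies the death.

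**Analysis sections.** Protocol 10.5.1.5 runs DOR from first response "to the date of first documented progression or death due to underlying cancer", so it counts progression or cancer death only, and adds: "Patients continuing without progression or death due to underlying cancer will be censored at the date of their last adequate tumor assessment". SAP 2.7.1 likewise ends DOR at "the date of the first documented progression or death due to underlying cancer". It says censoring follows the rule described for PFS, and then lists "options A(1), C2(1), D(1), E(1), F(1-3) and G(1) from Table 3-2 in Appendix 5 of the study protocol".

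**Protocol Appendix 5.** Section 3.2.6 gives DOR the same end date and censoring as time to progression, which by section 3.2.3 counts only deaths from the underlying cancer. Row G of Table 3-2 censors other deaths at the last adequate assessment, for time to progression and DOR only. Section 4.5.6 lists non-cancer death as a censoring reason for those two endpoints.

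**PFS.** Protocol 10.5.1.1 and SAP 2.7.1 count death from any cause.

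**Overall survival.** Both objectives tables state: "Overall Survival is defined as the time of start of treatment to date of death or lost to follow-up". Protocol 10.5.1.6 defines survival to death from any cause and adds: "If a patient is not known to have died, then OS will be censored at the date of last known date patient alive". SAP 2.7.1 agrees.

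**The concern.** The endpoint named in the objectives is not the one the analysis produces. Take a responder who dies of a treatment complication or an unrelated illness before any progression. By the tables, the response ended at death. By the analysis sections, it is treated as possibly continuing beyond the last adequate scan.

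Kaplan-Meier censoring assumes that the censored patient could still have the event later and resembles those still at risk. A patient who has died meets neither condition, so the curve describes a setting in which non-cancer deaths do not occur. Event status also depends on the recorded reason for death (study indication or other) in an open-label trial. A reader comparing median DOR with median PFS would not know that the two handle the same death in opposite ways, and the SAP's reference to the PFS rule would lead that reader to think they match.

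**Working it through.** The documents state no figure for DOR, so there is none to reproduce. The check is a comparison of the rules, followed by an illustration of size.

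**1. One patient under each rule.** A responder has a last adequate scan at time *a* and dies of a non-cancer cause at time *d*, with no progression recorded.

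| Source | Status | Time used |
|---|---|---|
| Protocol Table 3-1, SAP Table 1-1 (DOR) | event | *d* |
| Protocol 10.5.1.5, SAP 2.7.1, Appendix 5 row G (DOR) | censored | *a* |
| Protocol 10.5.1.1, SAP Table 2-5 (PFS) | event, unless two or more assessments were missed | *d* |

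The exception in the PFS row follows from SAP 2.7.3: a death is censored if the gap from the last adequate scan exceeds twice the interval plus twice the window, 2 × 12 + 2 × 1 = 26 weeks. Hence it is usually, not always, a PFS event.

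**2. The PFS label.** Row G does not apply to PFS, so a list containing G(1) cannot be the PFS rule. The same list gives F(1-3), three different treatments of new anticancer therapy, while SAP Table 2-5 uses only one for PFS (ignore the new therapy).

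**3. Direction.** Let *n* responders be at risk just after *a*, with *k* other events and no other censoring between *a* and *d*. From *d* onward:
- any-cause rule: the curve is multiplied by (n − k − 1)/n;
- cancer-death rule: the curve is multiplied by (n − 1 − k)/(n − 1).

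The ratio of the second to the first is n/(n − 1), above 1, so the cancer-death curve is higher from that death onward. With n = 30 it is 30/29 = 1.034.

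The figure of 30 is illustrative. The 26.5% partial response rate for PIK3CA-mutant patients in Protocol 1.2.5.2 gives 0.265 × 112 = 29.7. That rate comes from an earlier study across all dose levels, and Protocol 10.8 expects shorter PFS after a CDK4/6 inhibitor.

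**4. Size, under assumptions.** Assume constant hazards, and let *s* be the share of all any-cause endings that are non-cancer deaths. Then any-cause median = cancer-death median × (1 − s). Both *s* and the medians are assumed:

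| Cancer-death median | s = 2% | s = 5% | s = 10% |
|---|---|---|---|
| 8 months | 7.84 | 7.60 | 7.20 |
| 12 months | 11.76 | 11.40 | 10.80 |

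**5. Overall survival.** Protocol 10.5.1.6, Appendix 5 section 3.2.2 and SAP 2.7.1 all censor patients not known to have died at the date last known alive. Appendix 5 section 4.5.6 names loss to follow-up as a censoring reason. Only the two table cells differ.

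**The case against.** The strongest reply is that the DOR analysis to be run is not in doubt. The cancer-death rule appears in Protocol 10.5.1.5, in Appendix 5 section 3.2.6 and Table 3-2 row G, and in SAP 2.7.1, which names G(1). Both objectives tables send the reader to the analysis sections, and elsewhere the documents say any cause when they mean it. On this view the table cells are shorthand and need only a qualifier.

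Much of this stands. The rule is a deliberate default, and a reader should not infer that it is a slip. It does not remove the conflict: death without a qualifier ordinarily means any death, and the same summary appears in both documents. Nor does it explain the PFS label in SAP 2.7.1.

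Timing is also a fair objection. Enrollment was complete by 14-Dec-2020 and the Core Phase ends 19 months after last patient first treatment, so it should have ended before the protocol version of 28-Mar-2023. Changing the main definition now, in an open-label trial, would be post hoc. That is why the fix offers a second route.

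Two stronger readings are tempting. A reader might infer that censoring removes the deaths most likely to be drug-related. The documents say nothing about causes of death among responders; it is enough that such deaths could be included. A reader might also infer that overall survival has two event definitions, with losses counted as deaths. Every operative section censors losses, and the tables never call a loss an event.

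**Conclusion.** The concern holds for DOR. Two death rules stand in current text, and SAP 2.7.1 mislabels the one it applies. Relative to the endpoint in the objectives tables, the analysis as written shifts Kaplan-Meier DOR upward whenever a responder dies of another cause without progression. The amount cannot be calculated from the documents. The illustrated reductions of 2% to 10% in the median rest on constant hazards and assumed shares.

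The consequence is limited. DOR is a secondary, descriptive estimate in a non-comparative study, and Protocol 10.9 attaches no power to secondary variables. The primary endpoint, sample size and error rate are unaffected. The overall survival point is a wording correction only.

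**What to change.** **Preferred.** State one DOR death rule everywhere: first documented progression or death from any cause, matching both objectives tables and PFS.
- Amend Protocol 10.5.1.5 and SAP 2.7.1, and remove G(1) from the main DOR censoring list.
- Note in 10.5.1.5 that this overrides the Appendix 5 default (section 3.2.6, Table 3-2 row G and the DOR censoring reason in 4.5.6). Table 3-2 allows the protocol to depart from its defaults.
- Report the cancer-death-only version as a sensitivity analysis.

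**Alternative, if the cancer-death rule is kept as main because the data are mature.** Add the cause restriction to the DOR cell in Protocol Table 3-1 and SAP Table 1-1, remove the statement that DOR uses the PFS rule, and report any-cause DOR alongside.

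**Overall survival.** Delete the reference to loss to follow-up from the endpoint cell in both tables.

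**Cost.** Text edits and one additional Kaplan-Meier summary. Date and reason for death are already collected under Protocol 10.5.1.6. Under the preferred route, the reported median DOR may be slightly shorter.
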